Aim 3: Quantify LARC continuation over a 6-18 month follow-up period among LARC initiators within the SBHC network following implementation of telehealth-supported LARC provision. Using EHR data for all patients who initiated LARC, we will use Kaplan-Meier survival curves to assess LARC discontinuation overall, and Cox proportional hazard models to compare LARC continuation by LARC type.

Aim 3.1 (Primary Efficacy Outcome): 12-month continuation of LARC using telehealth-supported care among SBHC patients compared to LARC continuation rates among adolescents age 25 years and under as documented in a recent meta-analysis. Continuation rates will be expressed both as rates at 6 months and 12 months post-initiation, and using Kaplan-Meier curves to model discontinuation. Continuation rates in this setting will be compared to rates from a recent meta-analysis among adolescents and young adults that found 12-month continuation rates of 85.3% (primary efficacy outcome) for contraceptive implants and IUDs in the US-based studies (Usinger, Gola, Weis & Smaldone, 2016).

Aim 3.2 (Exploratory, pending feasibility) Continuation compared to pre-Telehealth. Compare 12-month continuation rate following introduction of telehealth to 12-month continuation among LARC initiators seen during the 18 month period prior to introduction of telehealth (June 2018-December 2019) *pending ability to export data from the prior electronic health record.*

Hypothesis:

We hypothesize that, in this sample of adolescents receiving telehealth-supported LARC services in a network of SBHCs, the LARC continuation rate at 12 months will be non-inferior to the 12-month continuation rate among adolescents and young adults age <25 (85.3%) as documented in a meta-analysis

comparing contraceptive implants and IUDs, in the absence of telehealth. The non-inferiority margin is chosen to be 10 percentage points less than that of the current standard of care (SOC) in US as such difference represents the maximum tolerable margin for inferiority while clinically important impact of proposed intervention can still be preserved.

Background/ Rationale

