Thematic analysis will be used to describe the qualitative data generated from the interviews. Using an inductive approach, two coders will scan a random selection of transcripts to generate initial codes; working from these, we will generate a code-book that lists major themes, specifies categories

emerging from the data, and descriptions of each theme. The first 10 transcribed interviews will be jointly coded using Dedoose; then, inter-rater coding agreement will be assessed. The entire study team will: resolve discrepancies in coding, clarify theme definitions, and collapse or expand themes as needed.

Primary efficacy outcome (Aim 3): Continuation post-LARC initiation

The primary outcome for this study (3.1) will be absolute continuation rate 12 months post-initiation (dichotomous yes/no continuation), with analyses also examining continuation at 6 months (yes/no).

Aim 3.1 (Primary Efficacy Outcome): Overall 12-month continuation of LARC using telehealth-supported care compared to LARC continuation rates among adolescents age 25 and under as documented in a meta-analysis of US studies.

The primary outcome will be the proportion of patients continuing their initiated LARC method at 12 months post-initiation. Hypothesis: We hypothesize that, with the non-inferiority margin of 10 percentage point difference, in this sample of adolescents receiving telehealth-supported LARC services in a network of SBHCs, the LARC continuation rate at 12 months will be non-inferior to the reported 12-month continuation rate among adolescents and young adults age under 25 years (85.3%) in the US who initiated contraceptive implants or IUDs the absence of telehealth (Usinger, Gola, Weist & Smaldone, 2016).

Statistical Methods (Aim 3.1):

Continuation rates will be expressed as rates at both 6 months and 12 months post initiation, and time to discontinuation will be visualized using Kaplan-Meier curves.

We will test the primary null hypothesis $H_0: p \leq 0.753$ (i.e., 10 percentage points less than the reference rate of 0.853) using one-sample, one-tailed Z-test, where p is the LARC continuation rate at 12 months for participants who receive telehealth-supported LARC services in a network of SBHCs, and the reference the proportion (of 0.853) was chosen from the finding of the meta-analysis mentioned above.

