Additionally, we will use Chi-squared tests to compare continuation (yes, continued/no, discontinued) between LARC types (contraceptive implant vs. IUD) at two time points: 6 months and 12 months post-initiation. Adjusted analyses using logistic regression will be conducted to compare the continuation at 6 and 12 months (yes or no) separately between contraceptive implant and IUD patients, adjusting for covariates (age, race/ethnicity, gender identity, sexual orientation, sexual activity in last 90 days, gravidity, parity). Operationalization of these covariates is outlined in Aim 1.

Power/Sample Size (Aim 3.1):

The study anticipates enrolling 113 patients, with 102 patients included in the continuation analyses for Aim 3 (primary outcome). Our sample size estimates are based on conservative SBHC clinical data from 2018-2019 and from the first seven months of 2019-20 (which was disrupted by both the transition to a new EHR Epic system and school and SBHC closures due to COVID-19); during the July 2018 to January 2020 time period, there were, respectively, 129 LARC initiations (86 contraceptive implant, 43 IUD), and 44 LARC initiations (41 implant, 3 IUD). These sample size estimates are conservative, as the SBHCs have three newly-hired and trained medical providers since the 2019-20 disrupted year.

We anticipate having complete data for the continuation analyses sample size ($n=102$). Using the new Epic EHR, at each visit within the NYP clinical network – the participating study sites in the SBHCs, as well as the emergency department, inpatient and outpatient clinics – the health care provider is required to conduct reconciliation of medications and document it in the Epic EHR. The medical providers ask every patient at every visit what their current contraceptive method is – confirming the presence of the method, and documenting in two places in the EHR (in the contraception and in medications sections). These analyses will be able to assess continuation (presence of the device at a visit) and censoring

(device removal, device removal with re-insertion).

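### Device removal is labelled as censoring, although discontinuation is the outcome of the planned Kaplan-Meier and Cox analyses

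*Combined protocol and SAP*

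**What the plan says.** All references are to the combined protocol and SAP.

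- **Outcome of the time-to-event analyses.** In Section 1, Aim 3 states "we will use Kaplan-Meier survival curves to assess LARC discontinuation overall", together with "Cox proportional hazard models to compare LARC continuation by LARC type". Aim 3.1 in the same section speaks of "using Kaplan-Meier curves to model discontinuation". In Section 2, Statistical Methods (Aim 3.1) repeats that "time to discontinuation will be visualized using Kaplan-Meier curves". Cox models are named only in Section 1.
- **Mapping of records to status.** Power/Sample Size (Aim 3.1), in Section 2, says: "These analyses will be able to assess continuation (presence of the device at a visit) and censoring". The bracket that completes that sentence reads "device removal, device removal with re-insertion".
- **Yes/no outcome.** The primary outcome is "the proportion of patients continuing their initiated LARC method at 12 months post-initiation", tested with a one-sample Z-test. For the comparison of device types, "we will use Chi-squared tests to compare continuation (yes, continued/no, discontinued) between LARC types", with logistic regression as the adjusted version.
- **Exported codes.** Section 3, Follow-up observation (Aim 3), plans to export insertion, removal and replacement procedure codes, device codes and all visits. It says these will identify events and censoring, but does not assign any code to either class.
- **Length of observation.** The maximum is 19 months in the paragraph of Section 2 on study phases. It is 18 months in Section 1 (Aim 3), in the opening of Section 2 and in Section 3 (Aim 3).

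**The concern.** In a survival analysis of discontinuation, removal of the device is the event. Calling it censoring means that the patient leaves the risk set without counting as a discontinuation. The same removal would then be a failure in the chi-squared table and a censored time on the curve in the same report.

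Removal with re-insertion is a different matter. Censoring it can be defended in an analysis at device level. The defect there is that it shares one class with plain removal and has no stated treatment of its own.

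The stake is the secondary person-time analyses. With even enrolment about half of the observation windows (51 of 102) end before month 12, so the Kaplan-Meier and Cox analyses are the ones that can use all 102 patients. Section 2 itself says that the continuation analyses rest on person-time. Their event code should not be open to two readings.

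**Working it through.** **1. The plan's own figure.** The plan gives no expected number of events. Its only related figure is 80% power at n = 102. With p0 = 0.753 and p1 = 0.853 (Statistical Methods and Power/Sample Size, Aim 3.1), and one-sided alpha 0.05 (not stated, but it reproduces the n):

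Φ[(0.10·√102 − 1.645·√(0.753·0.247)) / √(0.853·0.147)] = Φ[(1.010 − 0.709)/0.354] = Φ(0.849) = 0.802.

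This uses a yes/no outcome, so the censoring label does not enter.

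**2. Expected discontinuations, removal counted as the event.** Inputs: n = 102; true 12-month continuation 0.853 (the reference rate); windows uniform on 6 to 18 months (Section 3, Aim 3, with even enrolment assumed); constant hazard (assumed).

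- Hazard: λ = −ln(0.853)/12 = 0.1590/12 = 0.01325 per month.
- Mean probability of still continuing at window end: (e^(−6λ) − e^(−18λ))/(12λ) = (0.9236 − 0.7878)/0.1590 = 0.8539.
- Expected events: 102 × (1 − 0.8539) = 102 × 0.1461 = **14.9**, of which 13.2 fall by month 12.
- Cross-check with 12 full months for everyone: 102 × 0.147 = 15.0.
- At a true rate of 0.753 the same formula gives 102 × 0.2445 = 24.9.
- With a 19-month maximum, 14.9 becomes 15.5, so the 18 v 19 discrepancy matters little in size.

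**3. The same data, coded literally.** If every discontinuation is a removal, all are censored. There are 0 events, the Kaplan-Meier estimate is 100% throughout, and the Cox partial likelihood has no terms. This holds at either true rate, by construction.

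If a share m of discontinuations has no removal code, about 14.9 × m events remain: 1.5 at m = 10% and 3.0 at m = 20%. The simulated 12-month Kaplan-Meier means (3,000 replicates) are then 98.4% and 96.9%. The documents give no value for m, so these rows are assumptions only.

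**4. Cox comparison.** The past mix in Power/Sample Size (Aim 3.1) is 86 + 41 = 127 implants and 43 + 3 = 46 IUDs, an implant share of 127/173 = 0.734. With equal hazards, 14.9 events split into about 10.9 and 4.0. Coded literally, both become 0 if all are removals.

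**5. Removal with re-insertion.** Suppose 2% or 5% of patients have one by month 12, independently of discontinuation (assumed). Counting it as an event gives 0.853 × 0.98 = 83.6% or 0.853 × 0.95 = 81.0%. Censoring it, or counting it as continuing, leaves 85.3%.

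**6. Date of censoring, with removal as the event.** Simulated 12-month Kaplan-Meier estimates at a true 85.3% (3,000 replicates, Poisson visits; unseen discontinuers make no later network visit):

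| Censoring at | 0% unseen | 10% unseen | 20% unseen |
|---|---|---|---|
| End of window | 85.3% | 86.8% | 88.2% |
| Last visit, 5 visits a year | 82.4% | 84.1% | 85.5% |
| Last visit, 3 visits a year | 79.7% | 81.5% | 83.3% |

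Five visits is the 2018-19 average over all female patients (Section 3, Aim 3). A footnote in Section 4 expects fewer among LARC users without giving a number, so 3 is assumed, as are the unseen shares. The directions are general: window-end censoring overstates continuation if some removals are unseen, and last-visit censoring understates it if all are captured.

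**The case against.** The best defence is that nobody intends this. The sentence sits in a sample-size section and describes what the record system can capture. The aims and methods text names discontinuation as the outcome four times over, and Section 3 treats events as something wider than censoring. A flat curve beside a non-zero discontinuation rate would be noticed at once. No confirmatory claim or power figure changes.

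Much of this stands. Loose wording is the likeliest explanation, and the harm is confined to the Kaplan-Meier and Cox analyses. But the sentence is the only one that maps records to status, and followed as written it is wrong rather than merely short of detail. Correcting it after seeing a flat curve would be a decision made with the data in hand. Reading removal as the event also leaves removal with re-insertion without a rule.

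Three stronger readings are tempting, and the documents do not support them:

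- A reader might infer that literal coding would leave a known small number of events, say up to 3. Only 0 follows from the text, and only if every discontinuation is a removal. Any other count needs an assumed share without a removal code.
- A reader might infer that the primary test is compromised. It takes a yes/no proportion, so it is untouched unless the 12-month rate is read from the curve, which the plan does not say. That about 51 windows end before month 12 is a separate question about the primary denominator.
- A reader might infer that one censoring date is plainly correct. The choice between window end and last visit is a judgement, and its size rests on assumed visit rates and unseen shares.

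**Conclusion.** The point holds as an internal contradiction: removal is labelled as censoring in one section, while discontinuation is the time-to-event outcome in two others. It should be fixed before analysis.

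Taken literally, about 15 expected events become 0. The 15 rests on n = 102, a true rate of 85.3%, even enrolment over 6 to 18 months and a constant hazard. The 0 rests on every discontinuation being a removal. The primary Z-test, the chi-squared tests and the logistic models do not change. The difference between 18 and 19 months is real but moves the expected count only from 14.9 to 15.5. Confidence is high in the contradiction itself; there is no basis for saying that the literal coding would actually be used.

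**What to change.** Replace the sentence in Power/Sample Size (Aim 3.1) with wording to this effect, for the Kaplan-Meier and Cox analyses:

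- The event is discontinuation of the initiated method: removal without replacement, or documented absence of the device.
- Patients without an event are censored at the end of their observation.
- Removal with re-insertion is a class of its own, with one treatment stated in advance and consistent with the definition of the primary outcome, which refers to the initiated method.
- One maximum observation window is used throughout, reconciling 19 months with 18.

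Censoring at the last visit with confirmed device presence can be added as a sensitivity analysis, with a note that the two censoring dates err in opposite directions.

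The cost is a few lines of text and one extra curve. The codes and visit records needed are already in the planned export, so there is no new data collection and no change in sample size.

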With a sample size of 102 and the margin of non-inferiority of 10 percentage points, the proposed study has 80% power to declare the non-inferiority of the telehealth-supported LARC services in a network of SBHCs in a one sample, one-sided Z test. This power analysis is for the primary efficacy outcome of interest, i.e., LARC continuation rate at 12 months. The reference LARC continuation rate at 12 months of 0.853 was obtained from the meta analysis conducted by Usinger, Gola, Weis & Smaldone in 2016. The studies included in their meta-analysis collected sample in the US with participants in those studies being young women aged 25 years and younger using a range of contraceptive methods. Therefore, if the true LARC continuation rate at 12 months is 0.753 or higher, the study is adequately powered to establish the non-inferiority of telehealth-supported approach. In the CHOICE Project, 12-month continuation of Copper IUDs among participants age 14-19 was 75.6% (Rosenstock et al., 2012).

Aim 3.2 (Exploratory, pending feasibility) Continuation compared to pre-Telehealth. Pending examination of the feasibility of constructing a pre-telehealth research database using the prior EHR system, compared to continuation rates within the same network prior to the implementation of telehealth-supported care, we will compare 12-month continuation (yes/no) following introduction of telehealth to 12-month continuation among LARC initiators seen the 18 month period prior to introduction of telehealth (June 2018-December 2019) *pending ability to export data from the prior electronic health record.*

3. Study Procedures

AIM 1

Participant enrollment – Aim 1: All patients who receive care at the SBHC provide informed consent for care, as well as record review for quality assurance purposes. Analyses for Aim 1 will include all female patients who have a “reproductive health visit,” which includes contraceptive counseling, contraceptive management, or contraceptive method initiation, during the study period. All patients who have a telehealth consultation with a SBHC medical provider for LARC services (conservatively estimated n=113) will be considered enrolled patients once the data are extracted from the EHR, and these will inform uptake analyses for Aim 1.

AIM 2

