Follow-up observation (Continuation Analyses, Aim 3): Follow-up observation will continue for 6 months after the enrollment phase has completed; therefore, participants enrolled in the first month will have 18 total months observation, while those enrolled in the last month will have 6 months. In 2018-19, in the network of 6 SBHCs, 2,425 unique female patients had a total of 12,398 visits (for any purpose), representing an average of 5 SBHC visits per female patient in the academic year.² At each visit to the SBHC, regardless of visit type, all female patients have their medications, including contraceptive method, reconciled and confirmed in the medical record. With the new Epic EHR system, export of all LARC-related procedure codes (insertions, removals, removal with replacement) and device codes (e.g. Nexplanon, Liletta, Paragard) *in addition to all visits* (with corresponding data on current contraceptive method) will enable us to identify person-time events including censoring. At all New York Presbyterian (NYP) sites, the health care provider is required to conduct reconciliation of medications and document it in the EHR at every visit. The SBHC medical providers ask every SBHC patient at every visit what their current contraceptive method is – confirming the presence of the method, and documenting this in two places in the EHR (in the contraception history section, and in the medications section).

Compensation.

All Aim 2 survey and interview participants will receive compensation for their time and effort in the form of an Amazon electronic gift card, purchased through the Mailman School of Public Health. Compensation is as follows:

Quantitative survey participants will receive, as compensation for their time and effort, an Amazon gift card valued at \$10 at the conclusion of the survey. The card will be sent to participants electronically.

Qualitative interview participants will receive, as compensation for their time and effort, an Amazon gift card valued at \$25. The card will be sent to participants electronically.

4. Study Subjects

Subject Population Justification:

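### The power section claims adequate power from a true 12-month rate of 0.753 upward, but 0.753 is the null boundary; the 80% holds at about 0.853, and alpha and the test's variance form are not stated

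*Combined protocol and SAP*

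**What the plan says.** Statistical Methods (Aim 3.1) sets the primary null hypothesis at p ≤ 0.753, explained as "10 percentage points less than the reference rate of 0.853". It is to be tested "using one-sample, one-tailed Z-test, where p is the LARC continuation rate at 12 months".

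Power/Sample Size (Aim 3.1) states that with 102 patients and a 10-point margin "the proposed study has 80% power to declare the non-inferiority of the telehealth-supported LARC services". It adds that "The reference LARC continuation rate at 12 months of 0.853 was obtained from the meta analysis". It then concludes that "if the true LARC continuation rate at 12 months is 0.753 or higher, the study is adequately powered to establish the non-inferiority". The sentence after that cites an outside cohort in which "12-month continuation of Copper IUDs among participants age 14-19 was 75.6" percent.

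Neither section gives a significance level or says whether the standard error uses the null rate or the observed rate. Neither names the true rate at which the 80% was calculated.

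**The concern.** The power conclusion contradicts the hypothesis it is meant to serve. A true rate of 0.753 belongs to the null, so the chance of declaring non-inferiority there is held at alpha by design. Just above 0.753 it is barely larger. Because 0.853 appears only as the reference rate, the conclusion is the plan's only statement of which true rates the study is powered for, and that statement is wrong.

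Two things are at stake. First, a reader who relies on the sentence would take a failed test at a true rate of, say, 0.80 as the verdict of a well-powered study, when success was unlikely from the start. Second, with alpha and variance form open, the number of continuing patients needed for success is not fixed in advance. In a single-arm comparison with a fixed benchmark, that number is the whole decision rule.

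**Working it through.** **Inputs.** p0 = 0.753, margin 0.10 and reference rate 0.853 (Statistical Methods, Aim 3.1); n = 102, power 80%, one-sided Z-test (Power/Sample Size, Aim 3.1). Assumptions, because the plan does not give them: one-sided alpha 0.05 or 0.025; null or Wald (alternative) variance; true rate p1 = 0.853 for the 80%.

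**Formulas** (normal approximation).

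- Null variance: critical proportion c = p0 + z·√(p0(1−p0)/n); power = Φ((p − c)/√(p(1−p)/n)).
- Wald variance: power = Φ((p − p0)/√(p(1−p)/n) − z).
- Required N, null variance: ((z·√(p0(1−p0)) + 0.8416·√(p1(1−p1)))/0.10)².
- Required N, Wald variance: (z + 0.8416)²·p1(1−p1)/0.10².

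**Step 1: reproduce the plan's 80%.** p0(1−p0) = 0.1860, so the null standard error is √(0.1860/102) = 0.0427. p1(1−p1) = 0.1254, so the standard error at 0.853 is 0.0351. With z = 1.645, c = 0.753 + 1.645 × 0.0427 = 0.8232. Power = Φ((0.853 − 0.8232)/0.0351) = 80.2%.

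| One-sided alpha, variance | Power at 0.853, n = 102 | N for 80% | True rate giving 80% |
|---|---|---|---|
| 0.05, null | 80.2% | 101.5 → 102 | 0.8528 |
| 0.05, Wald | 88.6% | 77.5 → 78 | 0.8426 |
| 0.025, null | 67.9% | 130.7 → 131 | 0.8652 |
| 0.025, Wald | 81.4% | 98.4 → 99 | 0.8516 |

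Alpha 0.05 with null variance matches 102 exactly. Alpha 0.025 with Wald variance is close. Under either pairing, 80% belongs to a true rate of about 0.85.

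**Step 2: power across the true rates the sentence covers.**

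| True rate | 0.05, null | 0.025, Wald |
|---|---|---|
| 0.753 | 5.0% | 2.5% |
| 0.756 | 5.7% | 2.9% |
| 0.80 | 27.9% | 22.0% |
| 0.82 | 46.6% | 42.1% |
| 0.84 | 67.8% | 66.9% |
| 0.853 | 80.2% | 81.4% |

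Over all four pairings, power is 18–32% at 0.80 and 33–55% at 0.82.

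**Step 3: what result passes.** The smallest passing counts, with exact binomial size and power for n = 102:

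| Rule | Arises from | Size at 0.753 | Power at 0.80 | at 0.82 | at 0.853 |
|---|---|---|---|---|---|
| ≥ 84/102 | 0.05, null or Wald | 5.8% | 32.6% | 52.5% | 83.7% |
| ≥ 85/102 | 0.025, Wald | 3.5% | 24.0% | 42.3% | 76.3% |
| ≥ 86/102 | 0.025, null | 1.9% | 16.7% | 32.4% | 67.3% |

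The 84/102 result is marginal: its null-variance Z is 1.652 against 1.645. Its one-sided 95% lower bound is 0.7533 by the score (Wilson) method and 0.7614 by Wald, both above 0.753. By Clopper-Pearson it is 0.7496, which fails.

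**The case against.** The strongest reply is that the design calculation is sound and only one interpretive sentence is wrong. That is correct: 102 patients give 80% power at the reference rate under a conventional choice, and no change to the sample size is asked for on this ground.

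The gap in the test specification can also be overstated. At one-sided 0.05, null and Wald variance lead to the same rule, at least 84/102, so the 80.2% and 88.6% are two approximations to one rejection region with exact power 83.7%. Variance form changes the decision only if alpha is 0.025. The 86/102 cut-off needs a pairing with only 67.9% power, at odds with the plan's own 80%. If only the two pairings near 80% are admitted, 85/102 passes both and only 84/102 is disputed. So alpha is the main omission. It still has to be stated: the sample size is also described as set by patient flow, so the exact match at 102 suggests 0.05 with null variance but does not prove it.

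Three further points are fair. The sentence has no upper limit, and above 0.853 power does exceed 80% (about 92% at 0.87 under 0.05, null variance); the error lies in the part from 0.753 to the reference rate. Approximate power crosses 50% near 0.823, but exact power for the 84/102 rule crosses near 0.818. And the 75.6% figure is for copper IUDs only, while the SBHC initiations reported in the same section were mostly implants (86 of 129, then 41 of 44), so it is not an expected rate for this cohort. It only shows that a rate the plan itself cites lies inside the range called adequately powered, where the approximate chance of success is 3–6%.

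One could read the sentence as saying that the margin makes 0.753 tolerable. That describes the margin, whereas the sentence is about a true rate and about power.

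**Conclusion.** The concern holds. The statement that power is adequate from 0.753 upward is false under any alpha or variance form, because 0.753 lies in the null hypothesis. Under one-sided 0.05 with null variance and n = 102, the approximate chance of success runs from 5.0% at 0.753 to 80.2% at 0.853, and is below 50% for true rates under about 0.823. The 80% figure and n = 102 are sound at 0.853.

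Separately, the primary decision threshold is not fixed: 84, 85 or 86 of 102, depending on alpha and variance form. The percentages rest on the assumed alpha values and on all 102 patients having a known 12-month status. This must be corrected because it concerns the primary outcome.

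**What to change.** In Power/Sample Size (Aim 3.1), replace the sentence with, for example:

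> If 102 patients are evaluable at 12 months, a one-sided 0.05 Z-test with null variance has about 80% power (normal approximation) to reject p ≤ 0.753 when the true rate is 0.853, about 47% at 0.82, 28% at 0.80 and 5% at 0.753.

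The exact values for the resulting rule (83.7%, 52.5%, 32.6% and 5.8%) can be given beside these.

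In Statistical Methods (Aim 3.1), add one line with alpha, variance form and decision rule, according to what was intended:

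- One-sided 0.05, null variance: one-sided 95% score (Wilson) lower bound above 0.753, i.e. at least 84/102; exact size 5.8%, exact power 83.7% at 0.853.
- One-sided 0.025, Wald variance: at least 85/102; approximate power 81%, exact power 76%, exact size 3.5%.
- One-sided 0.025, null variance: at least 86/102; restate power as about 68%.

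Keep n = 102 conditional. The plan says "We anticipate having complete data for the continuation analyses sample size", but under Follow-up observation (Continuation Analyses, Aim 3) patients enrolled in the first month have 18 months of observation, "while those enrolled in the last month will have 6 months". If fewer than 102 can be evaluated at 12 months, recompute both power and cut-off.

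The cost is one replaced sentence and one added line. Enrolment and data collection do not change. The stated operating characteristics become less favourable.
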